#### **4.5.3 Statistical Comparisons with NHS Data**

Comparisons between treatment groups (high-dose ifetroban vs. NHS-supplemented placebo for DB period; all open-label ifetroban vs. NHS for open-label period) will be performed using the

Wilcoxon rank sum test for primary and key secondary efficacy endpoints. Results will be presented alongside the pre-specified DB randomized comparisons but will be clearly identified as supplementary analyses.

## **4.6 Technical and Formatting Issues**

### **4.6.1 Cross-References and Figure Numbering**

All cross-references within this document refer to sections, tables, and figures within this SAP unless explicitly stated otherwise. Figure and table numbers follow a consistent numbering system: Figure X-Y where X is the main section number and Y is the sequential figure number within that section.

### **4.6.2 Decimal Places and Rounding Rules**

The following conventions will be applied consistently throughout all analyses:

- Percentages will be presented to one decimal place
- Mean and median values will be presented to one decimal place more than the observed data
- Standard deviations will be presented to two decimal places more than the observed data
- P-values will be rounded to three decimal places; p-values <0.001 will be reported as "<0.001"
- Minimum and maximum values will be presented using the same number of decimal places as the collected data

## **5 SUMMARY OF STUDY POPULATION DATA**

### **5.1 Subject Disposition**

The following subject disposition variables, based on data reported on the screening disposition electronic case report form(eCRF), will be summarized (number and percent of subjects) by each treatment group and overall, for the safety population:

- Subjects screened
- Subjects completing the study and terminating early, with the reason for termination
- Subjects randomized, subjects in each study population and reasons for exclusion from the PP Population.

The disposition data will be listed by subject. along with protocol deviations.

## 5.2 Demographics and Baseline Characteristics

Demographic and baseline characteristics will be summarized by treatment group and overall.

Continuous demographic variables include age [years] at the time of informed consent, weight (kg), BMI (kg/m^2), and BMI z-scores.

Categorical demographic variables include BMI group (Underweight (<18.5), Normal weight (18.5-24.9), Overweight (25.0-29.9), and Obese ≥30), gender, race, ethnicity.

Categorical baseline characteristics variables are ambulatory (Yes/No), ventilatory support (Yes/No), stage of DMD (Late (35%-45%); Early (>45%)), Background DMD therapy (steroid alone, steroid + ASO (Exon-skipping therapy) ASO alone, none), and other cardiac medications (ACEi; ARB; ARNI; beta-blocker; diuretic; Aldosterone receptor antagonist; calcium channel blocker—outlined in the concomitant medication CRF; see [Table 1](#) below for complete listing of drugs in each class). Mutational analysis results will be included with age of DMD diagnosis.

Summary statistics for continuous variables will be presented as mean, standard deviation, minimum, median, and maximum, and for categorical variables, frequency counts and percentages.

A subject-data listing of demographics will be provided.

## 5.3 Dosing and Extent of Exposure

Exposure and compliance will be summarized for the Safety Population by treatment group and overall. Comments recorded on the Study Drug Accountability eCRF page will not be applied in the computation of compliance. Exposure is the duration (days) of treatment, computed as:

Exposure = Date of Final Dose - Date of Baseline Visit + 1.

Treatment compliance will be calculated as:

Compliance (%) = 100\*(Total Number of Capsules Dispensed-Total Number of Capsules Returned)/ (Expected Usage),

where Expected Usage= Exposure \* number of capsules to have been taken daily (1 capsule for 50 mg, 2 for 100 mg, 3 for 150 mg, or 6 for 300 mg).

Summary statistics for exposure and compliance will be presented in a table with the corresponding listing for the Safety Population. The number of subjects fasted at time of IMP administration for Month 6, Month 12 and both Month 6 and Month 12 will be summarized as categorical data (yes/no, %).

A subject-data listing of compliance will be provided.

## 5.4 Medical and Surgical History

The Medical History verbatim descriptions (investigator terms from the CRF) will be classified into standardized medical terminology using the Medical Dictionary for Regulatory Activities (MedDRA). Medical history will be coded to the MedDRA (Version 20.0 or higher) lower- level Term (LLT) to the closest verbatim term. The linked MedDRA preferred term (PT) and primary system organ class (SOC) will also be captured in the database.

The number (percent) of subjects will be presented by treatment and overall, and by SOC and PT for safety population.

A subject data listing of medical and Surgical history will be provided.

## 5.5 Concomitant Medications

Concomitant medications are defined as all prescription medications, over-the-counter drugs, and significant non-drug therapies administered after treatment through 30-days post study treatment must be recorded on the eCRF.

Concomitant medications will be coded in WHODrug GLOBAL C3 and listed by medication name and preferred term. Concomitant medications will be summarized by Preferred Term using the count and percentage of subjects by treatment group and overall for the Safety Population will be displayed. Subjects who have taken the same medication (in terms of PT) more than once will be counted only once for that medication.

Separate subgroup summaries will be provided for early stage DMD (LVEF > 45%) and advance (late) stage DMD (LVEF 35% - 45%) and combined (Early Stage + Late Stage).

All Concomitant medications will be presented in a listing for the Safety Population.

## 6 EFFICACY ANALYSIS

The efficacy analyses in this study incorporate natural history data as a supplemental comparator, a strategy supported by recent research and regulatory perspectives in rare disease settings. This approach has demonstrated validity in DMD specifically ([Goemans 2020](#)), where matched external controls have shown utility in drug evaluation, especially when disease progression is relatively well-characterized. The FDA has acknowledged the importance of natural history data in rare disease clinical development and real-world evidence frameworks. Research by Soslow et al. ([2023](#)) supports the application of natural history data while acknowledging its limitations and necessary methodological considerations. The propensity score matching methodology employed in this study aims to address potential selection bias and confounding factors when incorporating this external data.

All hypothesis tests will be performed at the 0.05 level. Analyses of secondary efficacy variables will be performed using the ITT and PP population only. Summary statistics will be presented for all analyses of efficacy variables.

## 6.1 Primary Analyses

Not Applicable

## 6.2 Secondary Analyses

Change from baseline endpoints and pharmacokinetics endpoints over 12 months included in the secondary analyses.

### 6.2.1 Change from baseline in LVEF and Myocardial Strain using CMR

The secondary analysis will focus on the change from baseline in LVEF and myocardial strain over 12 months of dosing.

The change from baseline in LVEF and myocardial strain will be compared between the treatment groups (High-Dose Ifetroban vs Placebo; Low-Dose Ifetroban vs Placebo) using Wilcoxon rank sum test for ITT population.

The number and change from baseline in LVEF and myocardial strain for each treatment group and overall, in the ITT population will be summarized descriptively. The following myocardial strain endpoints will be summarized:

- Indexed left ventricular end diastolic volume (LVEDVi)
  - LVEDVi = LVEDV/body surface area (BSA)
  - BSA calculation from CMR dataset using the Haycock method for pediatrics =  $0.024265 \times (\text{ht\_cmr})^{0.3964} \times (\text{wt\_cmr})^{0.5378}$
  - From CMR dataset: LVEDVi = “lvedv\_cmr”/ “bsa\_calc\_cmr”
- Indexed left ventricular end systolic volume (LVESVi)
  - LVESVi = LVESV/body surface area
  - BSA calculation from CMR dataset using the Haycock method for pediatrics =  $0.024265 \times (\text{ht\_cmr})^{0.3964} \times (\text{wt\_cmr})^{0.5378}$
  - From CMR dataset: LVESVi = “lvesv\_cmr”/ “bsa\_calc\_cmr”
- Mid Ecc (circumferential strain)

- Global Ecc
- Late gadolinium enhancement, full-width half-maximum (LGE FWHM)
- Number of segments with LGE (number of LGE segments with values >0)
- Base T1
- Mid T1

A subject data listing of all LVEF and myocardial strain will be provided.

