5.1 Background Information

5.1.1 Duchenne Muscular Dystrophy

Duchenne muscular dystrophy (DMD) affects approximately one of every 3,300 male births worldwide ([Quinlivan 2009](#)) and is caused by the complete absence of the sarcolemmal protein dystrophin as a result of anomalies in the X-linked DMD gene. Loss of dystrophin leads to inexorable damage to skeletal and cardiac muscle, with cardiomyopathy increasingly recognized as a major cause of death ([Romfh 2010](#)). Due to ongoing muscle damage, patients with DMD have markedly elevated serum levels of the muscle protein creatine kinase (CK), which may be 10× to over 100× the normal limit, and an elevated CK level is a diagnostic sign ([Konagaya 1986](#)). There is currently no cure for DMD. Current treatment is limited to the management of symptoms which is fueling investigations aimed at targeting the genetic defect. Several therapies are in various stages of development, including utrophin up-regulation, stop codon read-through therapy, viral gene therapy, cell-based therapy and exon skipping. These have mainly focused on improving skeletal muscle function without addressing the cardiac aspects of the disease, which may aggravate cardiomyopathy. For this reason, preclinical and clinical focus on improving heart function is essential.

The absence of dystrophin in the heart renders cardiomyocytes more sensitive to stretch-induced damage. This results in increased levels of intracellular calcium, thereby activating calpains and proteases that consequently degrade contractile proteins, promoting cellular death and fibrosis, all contributing to the development of cardiomyopathy ([D'Amario 2017](#); [van Westering 2015](#)). Animal and human data demonstrate the myocardial damage is evident before functional decline such as a reduction in left ventricular ejection fraction (LVEF) ([Rafael-Fortney 2016](#)), endorsing a strategic treatment window for initiating cardioprotective treatment at earlier stages of myocardial disease while EF is preserved. LV systolic strain measured by cardiac magnetic resonance imaging (CMR) is a more sensitive measure of cardiac function, has high reproducibility ([Soslow 2016](#)) – a critical feature when testing hypotheses in patients with rare diseases to support efficient sample size reductions – and is abnormal in even the youngest boys with DMD well before EF drops ([Hor 2009](#)). Eplerenone was recently shown using CMR to attenuate the decline

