11.1 Sample Size Determination

The sample size is based on the comparison of each dose level of ifetroban (Low Dose or High Dose) to placebo with respect to change from baseline in LVEF using CMR for each disease stage, early (LVEF > 45%) or advanced (current/historical LVEF 35-45%). Assuming observations from each treatment group have normal distributions with an effect size of 1.6 for the comparison of a dose of ifetroban to placebo, 8 subjects for each treatment group within disease stage will provide

power exceeding 85% for a t-test at two-sided level 0.05. Under these assumptions, 8 subjects for each treatment group within disease stage will provide power exceeding 80% for the Wilcoxon rank sum test at two-sided level 0.05. A total of 48 DMD subjects will be enrolled: 24 subjects with early stage DMD (LVEF > 45%) and 24 with advance stage DMD (current/historical LVEF 35-45%). Assuming a dropout rate of 25%, 60 subjects will be recruited to meet the target sample size of 48 subjects.

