### **3.4 Sample Size**

The sample size is based on the comparison of each dose level of ifetroban (Low-Dose or High-Dose) to placebo with respect to change from baseline in LVEF using CMR for each disease stage, early (LVEF > 45%) or advanced (LVEF 35-45%).

Assuming observations from each treatment group have normal distributions with an effect size of 1.6 for the comparison of a dose of ifetroban to placebo, 8 subjects for each treatment group within disease stage will provide power exceeding 85% for a t-test at two-sided level 0.05. Under these assumptions, 8 subjects for each treatment group within disease stage will provide power exceeding 80% for the Wilcoxon rank sum test at two-sided level 0.05.

A total of 48 DMD subjects will be enrolled: 24 subjects with early stage DMD (LVEF > 45%) and 24 with advance stage DMD (LVEF 35-45%). Assuming a dropout rate of 10%, 54 subjects will be recruited to meet the target sample size of 48 subjects.

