## 6.5 Subgroup Analyses

To assess the consistency of treatment effects across the subgroup levels, and to examine baseline biomarkers for their potential value to predict treatment response, exploratory subgroup analyses will be conducted for safety, tolerability, pharmacokinetics, and efficacy for the variables below.

The following subgroups will be assessed using the primary endpoint and primary endpoint related to clinical assessments, secondary endpoints, and exploratory endpoints.

- DMD disease stage (Early LVEF>45%, Late LVEF 35%-45%)
- Ambulation status (ambulatory vs non-ambulatory)
- Background therapy (none, steroids, ASO, steroids + ASO)

For each subgroup analysis, results will be presented as stratified analyses with descriptive statistics and treatment effect estimates within each subgroup level. Forest plots will be used to display treatment effects across subgroup levels for key endpoints. No formal statistical testing for interaction between subgroup and treatment will be performed due to limited sample sizes within subgroups, but the consistency of treatment effects across subgroup levels will be evaluated qualitatively. These analyses are considered exploratory and intended to identify potential patterns that may inform future research rather than to draw definitive conclusions about differential treatment effects.

Missing data in each factor, which will be limited if any, will not be included (as a separate group) in subgroup analyses. This does not apply to the PSM analysis.

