#### **14.3.4 List of Baseline Covariates for Modeling**

The following baseline covariates will be included in the DB and OL Model to create the propensity score.

- Age
- Baseline left ventricular ejection fraction (LVEF). Baseline will represent pre-treatment values in DB and Month 12 visit values will be the baseline in the OL study.
- Background DMD medications (current steroids, Current ASO/exon skipping)
- Additional cardiac medications (Aldosterone antagonists, Beta-blocker, ACEi, ARB, Calcium channel blockers, ARNI)

The following chart will be used to define the baseline med covariates in the NH dataset.

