#### **14.3.7 Analysis with Natural History Data**

Multiple analyses will be completed using matched NH subjects as a historical comparator. See [Figure 2](#) below for a detailed analysis diagram.

In the DB study (Baseline to Month 12), the tables will be presented by the following treatment groups:

- ifetroban High
- Placebo with supplemented NH

In the OL study, the tables will be presented by:

[figure not shown]
One year data (Month 12 to Month 24):

- All OL
- High to High ifetroban
- Low to High ifetroban
- Ifetroban (High and Low combined)
- Placebo to High ifetroban
- NH

All study two-year data (Baseline to Month 24):

- High to High ifetroban
- NH

**Figure 2** All Study Analyses Diagram

For both the OL and the DB, demographic and baseline characteristics will be summarized for by treatment group including baseline LVEF, concomitant medication usage and propensity score by treatment group for the DB period and the OL period. Summary tables will be provided for the observed value and the change from baseline for each endpoint. In addition, 95% confidence intervals will be presented for each treatment group for the demographic variables and baseline characteristics. For categorical variables, proportion confidence intervals will be created using the binomial approximation.

A listing of natural history subjects' demographic and baseline characteristics will also be included.

For the DB period, the endpoints CFB in LVEF and myocardial strain at 12 Months. For the OL period, the endpoints to be evaluated at the 24 months after treatment are CFB LVEF, CFB myocardial strain, PET, QMT, and accelerometry. All endpoints will be evaluated using the change from baseline will be compared between the ifetroban vs. Placebo or natural history groups using a Wilcoxon rank sum test

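### The randomised LVEF and strain tests do not use the baseline value and define no effect estimate; the natural history match omits the baselines of strain, lung function, strength and activity

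*SAP*

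**What the plan says.** **Randomised comparison.** SAP 6.2.1 states that "The change from baseline in LVEF and myocardial strain will be compared between the treatment groups", each dose against placebo, by Wilcoxon rank sum test. Protocol 11.8.3 names the same test. Neither section uses the baseline value as a covariate or defines a treatment difference with an interval. Pulmonary function (SAP 6.2.3) and muscle strength (SAP 6.3.1) are only summarised in this period.

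**Natural history comparison.** SAP 4.5.3 and 14.3.7 apply the same rank test to change. In the double-blind period it covers LVEF and strain. In the open-label period, "the endpoints to be evaluated at the 24 months after treatment are CFB LVEF, CFB myocardial strain, PET, QMT, and accelerometry" (PET is apparently a slip for PFT). The 95% intervals in 14.3.7 are per group and concern demographic and baseline variables, not the treatment difference.

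**Matching.** SAP 14.3.4 introduces its list with "The following baseline covariates will be included in the DB and OL Model to create the propensity score". The list, like SAP 4.5.1, holds age, baseline LVEF, and DMD and cardiac medications. Baseline strain, PFT, QMT and activity are absent. The main match has no caliper (SAP 4.5.2).

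**Where estimates are promised.** For subgroups, SAP 6.5 says "results will be presented as stratified analyses with descriptive statistics and treatment effect estimates within each subgroup level", with forest plots. No estimator is defined there or elsewhere.

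**The concern.** There are two separate issues.

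First, a test on raw change in small groups discards information carried by the baseline value, and a rank test alone yields a p-value. LVEF change is the endpoint that sizes the trial, yet the plan names no estimate of its treatment effect and no interval. The forest plots in SAP 6.5 would display a quantity that the plan has not defined.

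Second, the natural history groups are not randomised. Matching on LVEF need not align the groups on other measures. Protocol 5.1.1 says of strain that it "is abnormal in even the youngest boys with DMD well before EF drops", so two boys with the same preserved LVEF may start from different strain. The same holds for lung function, strength and activity. If the groups start apart on the endpoint, part of the difference in change may reflect the starting point and not the treatment.

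**Working it through.** **1. The plan's own figure.** Inputs (SAP 3.4, Protocol 11.1): 8 per group within stage, two-sided 0.05, and "Assuming observations from each treatment group have normal distributions with an effect size of 1.6". The stated results are "8 subjects for each treatment group within disease stage will provide power exceeding 85% for a t-test at two-sided level 0.05" and that the same number "will provide power exceeding 80% for the Wilcoxon rank sum test at two-sided level 0.05".

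- t-test: noncentrality 1.6 × √(8/2) = 3.2 on 14 df gives 84.5%, half a point under the stated 85%. The normal approximation gives 89.3%.
- Exact Wilcoxon test, 100,000 simulated trials: 82.2%, in line with the stated figure.

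**2. Precision lost in the randomised comparison.** Let s² be the variance at each visit and r the baseline to Month 12 correlation. The documents give neither, so r is an assumed range.

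- Variance of change: 2s²(1 − r)
- Residual variance after ANCOVA: s²(1 − r²)
- Ratio: (1 + r)/2

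The effect size on the ANCOVA scale is 1.6/√((1 + r)/2), with 13 df.

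| r (assumed) | Variance ratio | Saving | Noncentrality | Power, 8 v 8 |
|---|---|---|---|---|
| change score | 1 | – | 3.20 | 84.5% |
| 0.5 | 0.75 | 25% | 3.70 | 92.7% |
| 0.7 | 0.85 | 15% | 3.47 | 89.4% |
| 0.8 | 0.90 | 10% | 3.37 | 87.6% |
| 0.9 | 0.95 | 5% | 3.28 | 85.8% |

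With stages pooled at 16 per arm and an assumed effect size of 1.0, power goes from 78.1% to 88.4%, 84.3%, 82.2% and 80.1% for the same four correlations. If the effect really were 1.6, the pooled change-score comparison would already have 99.2% power. All these gains are against a t-test on change, not against the planned Wilcoxon test.

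**3. Is the randomised test biased?** In 30,000 simulated null trials of 16 v 16 for each r, the mean difference was about zero and the type I error of the Wilcoxon test was 4.7% to 4.8%. In the roughly 16% of trials with a chance baseline difference above 0.5 SD, the error rate was 6.5% (r = 0.9) to 11.4% (r = 0.5). So there is no bias on average, but there is exposure to chance imbalance.

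**4. Natural history comparisons.** Suppose there is no effect, linear regression to the mean, and a baseline difference D in an endpoint that was not matched. The change comparison then shifts by (r − 1) × D. For D = 0.5 SD this is −0.15 SD at r = 0.7 and −0.05 SD at r = 0.9. Type I error of the Wilcoxon test on change (8,000 simulations each, r from 0.9 to 0.7):

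| Groups | D = 0.5 SD | D = 0.75 SD |
|---|---|---|
| 16 v 32 | 6.3% to 8.3% | 7.4% to 14.0% |
| 16 v 48 | 6.7% to 9.1% | 8.3% to 16.0% |
| 40 v 80 (assumed open-label size) | 8.6% to 15.9% | 14.0% to 30.9% |

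The 48 is 16 placebo plus 32 natural history subjects. The 32 applies if the 2:1 ratio in SAP 14.3.1 describes the whole control group. D is an assumption in every cell.

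**5. Do the other planned analyses close the gap?**

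- Inverse probability weighting and the 0.2 caliper (SAP 14.3.8) are described only for the same propensity score. Exact matching is for feasible categorical variables.
- The whole-cohort sensitivity analysis (SAP 14.3.8) is adjusted, but its covariates are not named.
- The mixed-model slopes (SAP 6.4.2) address durability and name no covariate or contrast.

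None of them names the endpoint's own baseline as a covariate.

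**The case against.** The strongest reply has four parts.

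- **The test is the specified one.** The Wilcoxon test is in the protocol, the sample size was checked against it, and efficacy is secondary to safety. This is true, but it does not supply an estimate or an interval.
- **Group summaries are tabulated.** SAP 4.1 gives n, mean, SD and median by group, so a reader could work out a difference. This stands against any inference that the trial cannot say how large an LVEF effect is. What is missing is a pre-specified estimator with its interval.
- **ANCOVA is not always the less biased choice without randomisation.** If the groups differ stably at the start and decline in parallel, the change score is unbiased and ANCOVA is off by (1 − r) × D, the same size as in step 4 with the opposite sign. This stands in full. It is why the fix shows both estimates.
- **The inputs are assumed.** No correlation, SD or natural history baseline difference is given. At r = 0.9 the gain at 8 per group is 85.8% − 84.5% = 1.3 points. This also stands; the figures are ranges.

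A reader might also infer that no comparison at all accounts for the endpoint's baseline. The documents do not support that: the natural history comparisons of LVEF match on baseline LVEF, or on Month 12 LVEF in the open-label period.

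**Conclusion.** The point holds as two limited statements.

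1. The randomised LVEF and strain comparisons ignore the baseline value and define no treatment difference or interval. The cost is precision: 5% to 25% of the change-score variance for assumed correlations of 0.9 to 0.5, or about 1 to 8 power points at the plan's own 8 per group and effect size 1.6.
2. The natural history comparisons are open to bias from starting differences in strain (both periods) and in lung function, strength and accelerometry (open-label only). Size and direction cannot be fixed from the documents. The error rates above are illustrations under normal data, equal variances, linear regression to the mean and assumed differences.

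Two stronger readings are tempting and fail. Starting differences do not bias the randomised comparison on average, because randomisation prevents it. And the concern does not reach a randomised test of lung function or strength, because none is planned. The double-blind natural history comparison is also labelled supplementary in SAP 4.5.3, which limits the weight that will rest on it.

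**What to change.** **SAP 6.2.1.** Add an ANCOVA of change on treatment group and the baseline value of the same endpoint. Report the adjusted difference with its 95% CI, and name it as the estimate for the forest plots in 6.5. Keep the Wilcoxon test, with the Hodges-Lehmann difference and its CI.

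**SAP 14.3.7.** For strain, PFT, QMT and accelerometry, place the same own-baseline-adjusted difference with 95% CI beside the unadjusted change comparison. The baseline should be the value from which that change is counted: pre-treatment or Month 12. Include age. Include ambulatory status only if the natural history study recorded it, since neither Protocol 11.5 nor SAP 14.3.1 lists it. Tabulate the baseline balance of each endpoint between the compared groups; the observed-value tables already planned come close to this. Correct PET if PFT is meant.

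**Cost.** SAP text and modest programming. The natural history study collects CMR, lung function, QMT and accelerometry at its yearly visits (Protocol 11.5), so no new data are needed. There are two downsides. A linear model in small groups leans on its assumptions, which the retained rank test offsets. In the non-randomised comparisons the adjusted and change-score estimates rest on different assumptions and may disagree, so both should be shown.
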